#### **5.5.4 Analytic Methods for Categorical or Continuous-Valued Secondary Outcome and Safety Data**

For categorical data, comparisons will be made between treatment groups using standard chi-squared techniques as the primary approach. In particular, the Cochran-Mantel-Haenszel one degree of freedom test will be used to reflect the stratified randomization. Exact p-values and 95% confidence intervals by the point-probability method will be reported[1].

For continuous endpoints, standard analysis of covariance (ANCOVA) methods will be used as the primary approach to compare treatment groups at end of treatment with the following covariates: baseline value, binary indicator variables for the two highest-risk stratification levels used in the randomization (using the lowest-risk, i.e., rectum/pouch polyposis, group as the reference stratum), and a binary treatment indicator (1=combination treatment, 0=single treatment).

For ordered categorical data, a Kruskal-Wallis nonparametric test for ordered categorical response will be used to compare treatment groups[5].

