### 5.1.2. CPP-1X (Eflornithine) Pharmacokinetics

The dose of CPP-1X (daily oral dose of 750 mg for an adult) for CPP-310 was selected based upon its known pharmacology and evidence from clinical studies.

Time to peak concentration for oral eflornithine is 4-6 hours.

Absorption: for the oral solution is 54-58% and is unaffected by feeding status.

Distribution: no protein binding sites, crosses blood-brain barrier, volume of distribution is 0.3-0.35 liters/kg.

Metabolism: urinary recovery of unchanged drug as eflornithine is 86% and essentially not metabolized.

Excretion: renal excretion. Elimination half-life: 3-3.5 hours but once daily oral dosing of 500-750 mg is sufficient to maintain efficacy as indicated in several clinical trials.

Eflornithine pharmacokinetic references include, Abeloff, *et al.*, 1984, Haegele *et al.*, 1981, Meyskens, *et al.*, 1998, and Meyskens *et al.*, 2008.

[figure not shown]

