14. The follow-up will be done as phone call to the subject to review medical history, surgical history for any FAP-related surgical events, concomitant medications and adverse events.
15. A food frequency recall questionnaire will be administered at the screening/baseline, 12 and 24 month/EOT visits. US and Canada sites only.
16. A peripheral blood sample (5 mL, lithium heparin) will be collected at each of the following time points: pre-dose and 1, 2, 4 and 8 hours post dose.
17. A peripheral blood sample (10 mL, EDTA) will be collected at screening/baseline for pharmacogenomic analysis.
18. A random urine sample (15 mL minimum) will be collected at the screening/baseline, 6, 12, 18 and 24 month/EOT visits for polyamine analysis.
19. The follow-up will be done monthly as phone call to review endoscopic excisional procedures/surgical history for any FAP-related surgical events.
20. HRQoL surveys will include EORTC QLQ-C30 and QLQ-CR29, EQ-5D health utility index assessment, and modified Cancer Worry Scale. They will be collected at screening/baseline, 3, 6, 12, 18, and 24 month/EOT visits.
21. EOT visit will occur within 2 weeks off study treatment for any cause including completion of treatment at 24 months.
22. Subject needs to be in the supine position for 10 minutes prior to the EKG, including EKGs collected during PK sampling.
23. 2-EKGs will be done on the day PK samples are collected: 1) before pre-dose sample and prior to dose, and 2) before the 4 hr PK sample is obtained.
24. Medical history includes – standard review of major systems, with particular attention to cardiovascular, cerebrovascular, peripheral vascular, gastrointestinal and hearing issues. Interaction with outside physicians should be documented.
25. Urinalysis panel includes – color, clarity/appearance, specific gravity, pH, protein, glucose, ketones and blood.
26. Subjects completing the initial 24 month treatment without an FAP-related event and participating in the extension study must be consented at this visit. Go to Table 4, for month 24 additional extension procedures. For those subjects not participating in the extension study, this will be the end of treatment visit.

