14. A food frequency recall questionnaire will be administered at month 36 and 48/EOT visit. US and Canada sites only.
15. A random urine sample (15 mL minimum) will be collected at months 24, 30, 36, 42 and 48/EOT visits for polyamine analysis.
16. HRQoL surveys will include EORTC QLQ-C30 and QLQ-CR29, EQ-5D health utility index assessment, and modified Cancer Worry Scale. They will be collected at months 30, 36, 42 and 48/EOT visits.
17. EOT visit will occur within 2 weeks off study treatment for any cause including completion of treatment at 48 months.
18. Subject needs to be in the supine position for 10 minutes prior to the EKG.
19. Medical history includes – standard review of major systems, with particular attention to cardiovascular, cerebrovascular, peripheral vascular, gastrointestinal and hearing issues. Interaction with outside physicians should be documented.
20. Urinalysis panel includes – color, clarity/appearance, specific gravity, pH, protein, glucose, ketones and blood.
21. These procedures are in addition to those listed for Month 24 on the initial treatment schedule (Table 3).

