#### **8.2.6. Initial 24 Month Treatment Intervention Early Termination (+ 2 weeks)**

Within 2 weeks off final study pill treatment for any cause, all subjects will have a follow-up history and physical exam/review of body systems (including, weight and vital signs), along with toxicity assessment. Repeat blood laboratory tests (CBC, chemistry panel, and urinalysis), a random urine sample will be obtained for polyamine determination, EKG (Subject needs to be in the supine position for 10 minutes prior to the EKG) and audiometry will be performed. Women

of child bearing potential will also have a serum pregnancy test performed. Concomitant medications, adverse events and medication compliance will also be reviewed. Quality of life questionnaires (EORTC QLQ-C30, EORTC QLQ-CR29, EQ-5D and the modified Cancer Worry Scale) will be provided to the subject to complete. A food frequency questionnaire will be provided to the subject to complete at North American (United States and Canada) sites only.

Repeat upper and lower endoscopies with image and video documentation will be obtained at the Month 24/EOT visit or if the subject has completed at least 3 months of treatment from the previous on-study upper and lower endoscopy procedures (including baseline). A normal mucosal biopsy sample for polyamine determination will be obtained during the colonoscopy/proctoscopy procedure.

If the subject has an unscheduled upper/lower endoscopy for any reason, these procedures should be captured with image and video documentation including the collection of a normal mucosal biopsy, if possible. A random urine sample should be obtained for polyamine determination, if possible.

Subjects will be formally taken off-study treatment and complete the End of Treatment (EOT) assessments if there is a cumulative delay/suspension of study medication for any reason of:

- > 90 days from randomization to month 36
- > 105 days from randomization to month 42
- > 120 days from randomization to month 48

A temporary suspension from taking study medication as stated above (for example, due to a non-FAP disease related surgery or procedure), will be documented as a treatment delay and the subject will continue on study, on their original schedule.

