#### **8.2.7. Initial 24 Month Treatment Intervention Follow-Up (30-days post end of treatment visit +/- 1 week) Off Study**

Thirty-days (30) after completion of the end of study evaluations, subjects will be contacted by phone for a clinical update in regard to symptoms and interval medical history. Concomitant medications and adverse events will also be reviewed. The subject will provide a clinical update and procedure date for any FAP-related surgical event or major endoscopic excisional event that has occurred since the last contact. These include partial colectomy, colectomy with IRA, total procto-colectomy, proctectomy, pouch resection, sub-mucosal resection, trans-duodenal excision, ampullectomy, duodenectomy, or Whipple procedure.

An FAP-related event at any disease site (colon/rectum/pouch, duodenum) will lead to discontinuation of the study treatment but follow-up of the subject will continue until the end of the 30 day follow-up period.

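### Continuous secondary and safety outcomes are compared at end of treatment, a visit whose timing depends on the primary event, so if the combination delays events the arms are compared at different times since randomization

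*SAP*

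**What the plan says.** SAP 5.5.4, repeated in Protocol 12.6.3, names ANCOVA as the primary approach for continuous endpoints, "to compare treatment groups at end of treatment with the following covariates: baseline value". The other covariates are "binary indicator variables for the two highest-risk stratification levels used in the randomization" and a binary arm indicator. Time on treatment and event status are not in the model.

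The EOT visit has no fixed month. Protocol 8.2.7 states: "An FAP-related event at any disease site (colon/rectum/pouch, duodenum) will lead to discontinuation of the study treatment". Sections 8.2.11 and 8.2.14 say the same. Table 3, footnote 21 adds: "EOT visit will occur within 2 weeks off study treatment for any cause including completion of treatment at 24 months". Table 4, footnote 17 has the matching rule for the extension: "EOT visit will occur within 2 weeks off study treatment for any cause including completion of treatment at 48 months". For subjects without an event, treatment ends at month 24 if they do not enter the extension, at 36, 42 or 48 months according to randomization date (Protocol 4.2), or earlier through withdrawal or trial end.

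SAP 3.2.4 and 5.6 list polyamines and quality-of-life scores as other secondary outcomes but give no alternative model for their continuous values. SAP 5.5.6 analyses secondary data as collected, with last observation carried forward as a sensitivity analysis.

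**The concern.** A between-arm comparison of a continuous outcome has a clear meaning when both arms are measured at the same time after randomization. Here the measurement time is itself a consequence of the primary outcome, which the combination is meant to change. If it does change it, single-agent subjects are measured earlier on average and more often at a visit prompted by progression. Combination subjects are measured later and more often event-free.

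The adjusted difference then mixes any direct drug effect with elapsed time, length of exposure and the circumstances of an event. At stake are the aim in Protocol 4.9 of quantifying each arm's effect on quality of life, the polyamine comparisons in SAP 3.2.4, and safety measures such as audiometry, where exposure would be unequal. Neither the collected-data analysis nor carrying the last value forward restores a common time.

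**Working it through.** **Inputs.** Event-free at 24 months: 30% single agent, 60% combination (SAP 3.1). Exponential times (SAP Table 3.2). Design hazard ratio 0.4243 (SAP 5.3). 171 randomized (Protocol 3.2). Treatment stops at 90 events (Protocol 4.2). Caps 36, 42 or 48 months. Assumed: 57 per arm (171/3), one cap for all, no dropout.

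**The plan's own figures.** Monthly rate = −ln S(24)/24.
- Single agent: −ln(0.30)/24 = 0.05017, median ln 2/0.05017 = 13.817 months.
- Combination: −ln(0.60)/24 = 0.02128, median 32.566 months.

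Both match Table 3.2, and the rate ratio is 0.4243.

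**EOT at the design rates.** Mean EOT = (1 − exp(−rT))/r. Share of EOT visits set by the event = 1 − exp(−rT).

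| Cap T (months) | Mean EOT, single | Mean EOT, combination | Gap | Event share, single | Event share, combination |
|---|---|---|---|---|---|
| 36 | 16.7 | 25.1 | 8.5 | 84% | 54% |
| 48 | 18.1 | 30.1 | 11.9 | 91% | 64% |

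These shares cannot all occur in this trial. With 57 per arm they imply 57 × (2 × 0.836 + 0.535) = 126 events and 57 × (2 × 0.910 + 0.640) = 140 events, against a stop at 90.

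**Calibration to 90 events.** Solve 57 × [2(1 − e^(−H)) + (1 − e^(−0.4243H))] = 90 for the single-agent cumulative hazard H at the cap. This gives H = 0.970. The event shares are 1 − e^(−0.970) = 62% and 1 − e^(−0.4243 × 0.970) = 34%. Check: 35.4 + 35.4 + 19.2 = 90. With r = H/T for a single agent and 0.4243 H/T for the combination:

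| Cap T (months) | Mean EOT, single | Mean EOT, combination | Gap |
|---|---|---|---|
| 36 | 23.0 | 29.5 | 6.5 |
| 42 | 26.9 | 34.4 | 7.5 |
| 48 | 30.7 | 39.4 | 8.6 |

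**Sensitivity to six-monthly detection.** SAP 7.3 expects events to cluster at scheduled visits. If each event is found only at the next six-monthly visit, mean EOT = 6 × Σ S(6k), for k = 0 to T/6 − 1. The gap becomes 30.5 − 25.0 = 5.6 months (cap 36, from unrounded means) and 40.4 − 32.6 = 7.7 months (cap 48). It shrinks by about 0.9 months but remains.

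**What a gap can do.** The documents give no drift rate, so this is an assumption. An outcome with no direct drug effect that drifts 0.01 SD per month would show a spurious arm difference of 0.065 to 0.086 SD (0.01 × 6.5 to 0.01 × 8.6). At 0.05 SD per month it would show 0.32 to 0.43 SD. With no drift and no effect of the event itself, the spurious difference is zero.

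**If the arms do not differ in event times,** both follow the same EOT distribution and the expected gap is zero.

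**The case against.** The rule is generic, and the plan does not expressly assign this ANCOVA to polyamines, quality of life or laboratory values. Urinary polyamines draw on every study visit (SAP 3.2.4), quality-of-life sub-scales are classed by a 10-point change and described as trends (SAP 5.6), and toxicity comparisons use categorical methods (SAP 5.5.5). The secondary endpoints under type I error control are binary and fixed at months 6 and 12 (SAP 3.2.3). All of this is correct, and it confines the point to exploratory and safety analyses. It does not remove the point, because 5.5.4 is the only model stated for continuous secondary data and it names EOT.

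The design rates also overstate the size. They exceed the 90-event stop, and Protocol 3.2 reports 53 events by June 2017 and doubts that 90 will be reached. The calibrated figures are the ones to use, and with fewer than 90 events the event-driven shares would be smaller still.

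A reader might infer that EOT polyamines are measured without drug effect, since the visit may fall two weeks after the last dose and Protocol 5.1.2 says "Elimination half-life: 3-3.5 hours but once daily oral dosing of 500-750 mg is sufficient". The documents do not support that. The same sentence treats once-daily dosing as adequate despite the short half-life, and Protocol 2.4 describes irreversible inhibition of the target enzyme. No rate of polyamine recovery is given, so counting plasma half-lives does not measure lost suppression. Two weeks is also a maximum. Tissue is less exposed than urine: when a scheduled endoscopy finds the event, the biopsy comes from that on-treatment procedure, and an early-termination endoscopy is conditional on three months' treatment since the last one (Protocol 8.2.6). What stands is narrower: an EOT urine sample may be off drug, and the plan does not separate it from on-drug samples.

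**Conclusion.** The concern holds for continuous secondary and safety outcomes. If treatment delays events as designed, the stated rule compares arms at unequal times since randomization and with an unequal mix of event and event-free subjects. At 90 events and hazard ratio 0.4243, the event sets EOT for about 62% versus 34% of subjects, and mean EOT differs by about 6.5 to 8.6 months. The uncalibrated design rates give 8.5 to 11.9 months. These figures rest on 57 per arm, exponential times (SAP 5.3 itself doubts constant hazards), a single cap for all and no dropout.

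The resulting bias in any particular outcome is unknown, because it depends on drift and event effects that the documents do not give. A reader might infer that the trial's main conclusions are at risk. They are not: the primary log-rank test, the sample size and the UGIOI and LGIOI endpoints do not use this rule. The change is worth making before analysis, but it does not threaten the trial.

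**What to change.** In SAP 5.5.4 and Protocol 12.6.3, replace the EOT comparison with a fixed scheduled visit. Use month 12 as the main contrast, in line with the SAP's own month 6 and 12 endpoints, and also report month 6 where it is collected, because fewer subjects have left by then. Estimate it from a repeated-measures model with baseline, stratum, arm, visit and arm-by-visit, using each outcome's own on-treatment schedule:
- Quality of life and laboratory values: months 3, 6, 12, 18, 24 and later.
- Urine and tissue polyamines: months 6, 12, 18, 24 and later (there is no month-3 sample).
- Audiometry: ANCOVA or the same model at months 12, 24 and later.

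Report EOT values descriptively. State that an EOT visit coinciding with a scheduled visit, such as month 24 for subjects who do not extend, counts as that scheduled visit. For EOT urine polyamines, record days since last dose and exclude samples taken after dosing stopped from the on-treatment contrast.

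The cost is SAP and protocol wording and a standard model on data already scheduled. The downside is that subjects with an event before the chosen visit contribute only earlier visits, and more of them are on single agents. At the calibrated 36-month rates (0.970/36 = 0.0269 and 0.4243 × 0.0269 = 0.0114 per month), 1 − exp(−12r) gives 28% versus 13% with an event by month 12, and 1 − exp(−6r) gives 15% versus 7% by month 6. The analysis then relies on a missing-at-random assumption, which the SAP should state.

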## 3. STUDY OBJECTIVES AND ENDPOINTS

### 3.1 Overview of Study

This is a randomized, double-blind, phase III trial in patients with FAP to evaluate the safety and efficacy of the combination product 750 mg CPP-1X + 150 mg sulindac versus each of the two single-agent products: 1) 750 mg CPP-1X; and 2) 150 mg sulindac. The primary study comparisons will be made between the combination product and each single agent product, separately.

Eligible patients who have given informed consent will enter the study with the intent to participate for the full treatment period of 24 months. Based on a subject's date of randomization, patients will be offered continued preparticipation in blinded treatment for up to a total of 36, 42 or 48 months of treatment if they have completed the initial 24 months of treatment without an FAP event until one of the following occurs: 1) subject has an FAP event or comes off study for other reasons, 2) all randomized subjects have reached a minimum of 24, 36, 42 or 48 months of treatment.

A stratified randomization procedure will be used based on FAP-related time-to-first-event prognosis. The event prognosis groups are represented by 1) best (i.e., longest projected time to first FAP-related event) - rectal/pouch polyposis, 2) intermediate - duodenal polyposis, and 3) worst - pre-colectomy. If a subject has two or more of these disease sites, the most severe prognosis stratum will be assigned for randomization (e.g. worst > intermediate > best). Since an individual may have more than one disease site involved, the trial will assess time to any defined FAP-related event in the patient as a whole. In order to minimize potential treatment arm imbalance a centralized randomization process will be used to balance treatment groups within disease prognostic strata.

The stratification is predicated on the following projected event rates for the disease site specific eligibility criteria (rectal/pouch polyposis, duodenal polyposis, pre-colectomy) which are provided in the clinical study protocol (Appendix E) and summarized in Table 3.1.

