**Table 3.1 Projected Event Free Rate by Disease Site**

Disease Site	Projected 2-year Event Free Rate Without Treatment
Rectum/Pouch Polyposis	Excisional intervention and/or high risk adenoma – 40 - 60%
Duodenal Polyposis	Excisional intervention, Spigelman stage progression, cancer – 50%
Pre-colectomy	Colectomy, proctocolectomy – 10%

The stratified randomization will be reflected in stratified analyses for the primary and secondary endpoints. For design purposes only, however, the following simplified assumptions were made: an overall event free proportion of 30% in the single agent treatment group and 60% in the combination treatment group after 24 months of study treatment. This is described further in Table 3.2 below. See Section 5.1 for sample size and power calculations.

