These binary UGIOI and LGIOI secondary efficacy endpoints will be compared in a manner analogous to the primary analysis, using the same two primary treatment comparisons (1: CPP-1X placebo + sulindac active vs. CPP-1X active + sulindac active; and 2: CPP-1X active + sulindac placebo vs. CPP-1X active + sulindac active), and conditioning on the three disease site strata (Rectum/Pouch Polyposis, Duodenal Polyposis, Pre-colectomy). The null hypothesis of no association between treatment group and Improvement endpoints will be tested using the exact Mantel-Haenszel procedure for combining the evidence contained in the fourfold tables (Treatment=Single agent vs. Combination cross-classified by Improvement=YES vs. NO) across the three strata. For each of the two treatment comparisons, exact Mantel-Haenszel p-values will be calculated for both the UGI and LGI assessments (using the point-probability method based

on the convolution of three independent central hypergeometric distributions; see [1]).

The overall type I error for the secondary efficacy analysis will be controlled using the Hochberg step-up method for multiple comparisons[2]. This analysis will be performed in the ITT population. The primary analysis will serve as a gatekeeper to control the overall type I error rate at 0.05 for both primary and secondary analyses. That is, significance for the secondary efficacy analysis will be declared only if the primary p-value is 0.05 or less, when the p-values are tested sequentially per the Hochberg method[2].

Further analyses of the secondary endpoints may be conducted to evaluate and provide additional evidence to support its validity and confirm its clinical relevance.

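### Ordered categorical outcomes get a Kruskal-Wallis test with no strata, although the neighbouring methods and SAP 3.1 call for stratified analysis (minor; free to improve)

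*SAP*

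**What the plan says.** SAP 3.1 sets up the design: "A stratified randomization procedure will be used based on FAP-related time-to-first-event prognosis". The strata are rectal/pouch polyposis, duodenal polyposis and pre-colectomy. After Table 3.1 the same section adds: "The stratified randomization will be reflected in stratified analyses for the primary and secondary endpoints".

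SAP 5.5.4 then gives one rule for each type of secondary and safety outcome:

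- Categorical: "In particular, the Cochran-Mantel-Haenszel one degree of freedom test will be used to reflect the stratified randomization".
- Continuous: ANCOVA whose covariates include "binary indicator variables for the two highest-risk stratification levels used in the randomization".
- Ordered categorical: "For ordered categorical data, a Kruskal-Wallis nonparametric test for ordered categorical response will be used to compare treatment groups".

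Protocol 12.6.3 has the same three rules. Neither document adds strata to the third rule elsewhere. The two named secondary efficacy endpoints, UGIOI and LGIOI, are binary. SAP 3.2.3 tests them by an exact Mantel-Haenszel procedure across the three strata, once for each single agent against the combination.

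**The concern.** Two of the three rules in SAP 5.5.4 follow the stratified randomisation and the third does not. Kruskal-Wallis as usually defined has no blocking factor, so a programmer following the text would run it unstratified.

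Randomisation within strata keeps differences between strata largely out of the treatment comparison, but an unstratified rank test still counts them as noise. If the strata predict the outcome, the standard error is too large, the actual level falls below 0.05 and power is lost. The strata were chosen as prognostic: Table 3.1 projects 2-year event-free rates of 40-60%, 50% and 10% for rectum/pouch, duodenal and pre-colectomy disease.

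The outcomes that could be affected are ordinal ones below the alpha-controlled tier. Examples are the blinded 5-point global endoscopic assessment (Protocol 9.3), the improved or deteriorated HRQoL classes (SAP 5.6) and adverse-event severity, if compared between arms. For a safety comparison, a conservative test makes a real difference harder to see.

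**Working it through.** **The plan's own figures.** Neither document gives a level or power for the Kruskal-Wallis analyses, so there is nothing to reproduce for this point. The primary design figure does reproduce. Schoenfeld's formula, 4(1.960 + 1.036)²/(log HR)², gives 49 events at HR 0.4243 and 25 at log(0.70)/log(0.30) = 0.296, matching the stated 25 to 49. That calculation does not involve the ordinal outcomes.

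**Inputs from the documents.** 171 randomised 1:1:1 (Protocol 3.2, 4.3), so 171/3 = 57 per arm if equal; three strata; Table 3.1 event-free rates.

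**Assumptions, not in the documents.** Five ordered categories, exact balance within strata, stratum sizes, stratum shifts, and a treatment effect of 0.53 SD.

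**Tests compared, for one pair of arms.** The unstratified statistic is Z = [R₁ − n₁(N+1)/2]/√V. Here R₁ is the rank sum in one arm and V is the tie-corrected variance over all N patients. With two groups, Kruskal-Wallis equals Z². The van Elteren statistic ranks within each stratum k and combines with weights wₖ = 1/(Nₖ+1): Z = Σwₖ[R₁ₖ − n₁ₖ(Nₖ+1)/2]/√(Σwₖ²Vₖ).

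**Hand approximation.** Take equal strata with only pre-colectomy shifted, by δ within-stratum SDs. The variance between strata is B = (1/3)(2/3)δ² = 2δ²/9. The unstratified test at 1.96 then behaves like a stratified test at 1.96√(1+B). A stratified power of 0.75 corresponds to a mean Z of 1.960 + 0.674 = 2.634, and 0.74 to 1.960 + 0.643 = 2.603.

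| δ | B | effective cut-off | level | approximate unstratified power |
|---|---|---|---|---|
| 0.5 | 0.056 | 2.014 | 0.044 | Φ(2.634 − 2.014) = 0.73 |
| 0.75 | 0.125 | 2.079 | 0.038 | Φ(2.603 − 2.079) = 0.70 |
| 1.0 | 0.222 | 2.167 | 0.030 | Φ(2.603 − 2.167) = 0.67 |

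**Simulation of the same case** (57 v 57, equal strata, 4,000 replicates):

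| δ | unstratified power | stratified power | loss before rounding |
|---|---|---|---|
| 0.5 | 0.73 | 0.75 | about 1 point |
| 0.75 | 0.71 | 0.74 | about 3 points |
| 1.0 | 0.67 | 0.74 | about 6 to 7 points |

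Each simulated power has a standard error of about √(0.7 × 0.3/4,000) = 0.007, so the losses are good to roughly a point. With a smaller pre-colectomy stratum (26/20/11 per arm) the loss is about 0 to 4 points. With no stratum effect, the unstratified and stratified powers are 0.751 v 0.747 in one run and 0.750 v 0.748 in another.

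**Sensitivity** (proportional-odds model, log odds ratio 1.0, three assumed stratum mixes, 40,000 runs, 57 per arm). Here the strata are shifted by the logits of the Table 3.1 rates. For 50/50/10 the pre-colectomy shift is ln(0.1/0.9) = −2.197, or 2.197/1.814 = 1.21 logistic SDs.

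| Stratum effect | level, unstratified | power, unstratified v stratified | loss (points) |
|---|---|---|---|
| 60/50/10 | 0.019-0.032 | 0.67-0.75 v 0.82 | 7-14 |
| 50/50/10 | 0.022-0.035 | 0.70-0.77 v 0.82-0.83 | 6-12 |
| half of 50/50/10 | 0.041-0.047 | 0.81-0.82 v 0.83 | 1-3 |
| none | 0.048-0.049 | 0.84 v 0.84 | none |

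Across all of these 57-per-arm scenarios the stratified test holds a level of 0.048 to 0.052.

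**The case against.** The strongest reply is that no endpoint is shown to be affected. The documents name no ordinal outcome to be tested this way. The −2 to +2 investigator scores feed the binary UGIOI and LGIOI endpoints, and their month-6 and all-visit versions are only to be tabulated (SAP 3.2.4). SAP 5.5.5 compares adverse events only where appropriate, by the methods for categorical data, which can be read as the stratified CMH rule. This stands, and it is why the point is minor. The rule is still part of the plan for whatever ordinal data are tested, and SAP 5.6 calls the HRQoL sub-scales secondary endpoints, which brings them within the SAP 3.1 statement.

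A reader might also infer more than the text supports:

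- **That the test is a three-arm test.** SAP 5.5.4 says only that treatment groups are compared. Kruskal-Wallis also works on two groups.
- **That the ANCOVA pools the two single-agent arms**, because of "a binary treatment indicator (1=combination treatment, 0=single treatment". SAP 3.2.3 and 7.3 use single agent in the same shorthand within separate two-arm comparisons, so this is at most a wording point.
- **That SAP 3.1 promises stratified safety analyses.** It names primary and secondary endpoints only. For safety, the inconsistency is with the neighbouring rules in 5.5.4.
- **That the power loss is large.** Equal steps of 1.0 SD between adjacent strata give power of about 0.52 against 0.72, but that puts the outer strata 2 SD apart. Table 3.1 has rectum/pouch and duodenal disease about equal and only pre-colectomy apart. It also concerns time to FAP event; nothing in the documents says the strata predict change scores, toxicity grades or HRQoL items.

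**Conclusion.** The inconsistency is real and small. That the test is unstratified is inferred from the absence of any strata in the rule; the SAP does not use the word.

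If only the pre-colectomy stratum differs, by 0.5 to 1.0 SD, the unstratified test loses about 1 to 6 points of power (57 per arm, 0.53 SD effect). The loss is larger if the strata are further apart: about 6 to 14 points at 57 per arm if the ordinal outcome depends on stratum as strongly as Table 3.1 projects for the primary event. It is nil if the strata are not predictive. All of this rests on assumed shifts and stratum sizes, so the direction is firm and the size is not.

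The error is on the conservative side and cannot produce a false claim of benefit through an inflated level. No primary or alpha-controlled secondary result depends on it.

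**What to change.** In SAP 5.5.4 and Protocol 12.6.3, replace the Kruskal-Wallis test for ordered categorical outcomes with a van Elteren test (the CMH row-mean-score test with modified ridits), stratified by the three randomisation strata. State that it is run separately for sulindac v combination and for CPP-1X v combination. If wished, add a clause saying that the ANCOVA is fitted for the same two pairs.

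The cost is a sentence in each document and one procedure option in SAS. No new data or patients are needed, and stratifying costs essentially no power even when the strata are not predictive. The change is easiest to defend if made before unblinding.
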